Appendix J- Holiday Card

Appendix K- Outcome Reminder

Version 1.0 1.31.2020

[figure not shown]
Hello from Reach Out!

Thank you so much for taking part in Reach Out! We are delighted to walk with you on your journey to reduce your blood pressure.

It is time for your 6-Month Reach Out visit. This is a meeting with someone from our study team where we will take your blood pressure and complete a survey. It will take about 20 minutes, and you will be given \$25 for your time. Please drop in anytime:

Flint Farmer's Market XXAM-XXPM DATE.

If you are unable to meet on DATE, we will contact you to schedule another time and location to meet.

These visits are important for our study, so that we can know how you are doing. Thank you for your time and participation in Reach Out!

Sincerely,

[name]

Appendix L- Newsletter Outline

February 2020
Volume 1, Issue 1

Dear Reach Out Participant,

We want to update you on the progress of the Reach Out study and thank you from the bottom of our hearts for your continued support and participation. This newsletter contains info about:

- Outcome Visits
- Staff spotlight

Reach Out began recruitment in 2019. We have had an overwhelming response. We have enrolled over 800 participants. We are beginning doing 6 and 12 month outcomes.

Outcomes: Call us!

Please remember that we would love to meet with you after 6 months and again at 12 months to have a 20 minute visit to see how you are doing. At 6 months you will get \$25, and at 12 months you will get \$30. These visits are important for our study, so that we can know how you are doing. Please drop in anytime:

Flint Farmer's Market XXAM-XXPM DATE

If you are unable to meet on DATE, please call or text to pick a day and time!

Staff Spotlight: [name]!

It's amazing to see how awesome Reach Out is being received by the Flint Community. During a routine visit to my local Flint nail salon, I was chatting with my nail tech about work and how things had been going since moving to the area.

Another customer in the salon, overheard our conversation and been expressing her appreciation for Reach Out and how much she enjoyed the program.

She detailed the text messages received and the healthy life style tips she acquired. Her testimony sparked more conversation amongst others in the salon, and before I knew it everyone was asking me how they could sign up! It was incredible to hear how much we were influencing one particular person, but also to see the potential impact we could have on the community.

BLOODPRESSURE
DOCTOR
EXERCISE
FLINT
GREATJOB
HEALTHY
HURLEY
HYPERTENSION
MEDICATION
MEDITATION
REACHOUT
TEXT
VEGETABLES

Appendix M- Tele Outcome Reminder

Version 1.0 3.20.2020

HUM00138470/ 1199877

|
Hello from Reach Out!

Thank you so much for taking part in Reach Out! We are delighted to walk with you on your journey to reduce your blood pressure. The COVID-19 pandemic has caused Reach Out to change the way we are going to check-in with you. For your safety, we are going to collect your outcomes via picture and text message rather than in-person.

It is time for your 6-Month Reach Out outcome measurement. It will only take a few minutes and you will get \$25 for your time! Detailed instructions are on the next page.

These outcomes are really important for our study. They help us understand how you are doing and learn your thoughts on how Reach Out works for you.

Thank you for your time and participation in Reach Out!

Sincerely,
[name]

Version 1.0 3.20.2020

HUM00138470/ 1199877

|
Hello from Reach Out!

Thank you so much for taking part in Reach Out! We are delighted to walk with you on your journey to reduce your blood pressure. The COVID-19 pandemic has caused Reach Out to change the way we are going to check-in with you. For your safety, we are going to collect your outcomes via picture and text message rather than in-person.

It is time for your 12-Month Reach Out outcome measurement. It will only take a few minutes and you will get \$30 for your time! Detailed instructions are on the next page.

These outcomes are really important for our study. They help us understand how you are doing and learn your thoughts on how Reach Out works for you.

Thank you for your time and participation in Reach Out!

Sincerely,
[name]

Appendix N- Tele Outcome Guide

Version 1.0 3.20.2020 HUM00138470/ 1199877

Instructions for Outcomes

It is time for your 6- month outcome! It will only take a few minutes. You will be mailed \$25 for completing the outcome. For assistance, questions, concerns or you would like a Reach Out Team member to walk you through the outcome, feel free to call Reach Out at [contact].

What you need to do!

1 Step 1: Take a photo of yourself wearing the blood pressure cuff!

1. Open your camera app.
2. Place the blood pressure cuff on the **inside** of your wrist.
3. Aim the camera towards your wrist with the cuff on it.
 - i. We only need to see your wrist and that the cuff is on your wrist. We do NOT need to see your face.
4. When you're ready to take a photo, tap the shutter button located in the middle of the screen to take the photo.

Version 1.0 3.20.2020 HUM00138470/ 1199877

[figure not shown]
2 Step 2: Send us that photo!

1. Open your camera app.
2. Tap the picture you'd like to text.
3. Tap the share button on your screen. This looks different depending on the phone you are using.
 - i. If **iPhone**, it will be in the lower left corner.
 - ii. If **Android**, it may be in the middle of the top of your screen.
4. Send your photo to [contact].

If you have any trouble at all, call us! [contact]

3 Step 3: Text us 3 different blood pressures (xxx/xxx)!

1. Take your blood pressure using your blood pressure cuff. Follow the instruction sheet for taking your BP.
2. Text your BP to [name] as XXX/ XXX.
3. Follow the instructions sheet for text messages.
 - a. This is a text message and does not have to be a picture.

You will receive a confirmation that your outcome was completed within 24 hours.

Thank you for completing your 6-month outcome with Reach Out! You will receive your \$25 incentive within 10-20 business days. To confirm your address, call or text Reach Out at [contact].

If you have any trouble at all, call us! [contact]

Thank you!
[name]

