messages may be sent the 2 days before and the day of the outcome assessment. In striving for equity within our study population, we may also offer transportation credit to participants via a driving service, which is most readily available in that targeted neighborhood (taxi, public transportation, or ride share services are all possibilities), to be able to assess our primary outcomes of BP in person. Outcomes may be built into REDCap. Outcomes may be visually modified, questions removed, rearranged, or re-worded as resources become available, but the messaging, and content will remain consistent. Outcomes will be assessing such topics as contact/tailoring information, provider topics, medication, medication adherence, hospital use, the impact of coronavirus, and Reach out study feedback/ utilization. To increase retention for outcomes, and as already addressed within our enrollment process with participants, we may also be mailing 6/12 outcome reminders (Appendix K), and/or newsletters (Appendix L). Outcome reminders will be updated for either 6 or 12 month outcomes as needed. These materials are included as appendices in the protocol, and will be submitted to the IRB as outlines of materials. However, the dates, time sensitive information, and content may change as needed to better communicate and stay up to date with participants. For example, within the newsletters that may be periodically sent out and updated, it will always contain topics such as recruitment updates, 6/12 outcome visit information, study staff spotlights, end of study instructions, and any other relevant, time-sensitive informational updates. Given the topics and theme of the content will remain consistent, we will not submit changes to the IRB unless there are significant additions or deviations from topics.

7.1.2 **Tele-Outcomes**

Given recent COVID-19 precautionary contact recommendations or when unable or not recommended to conduct in-person 6 and 12 month outcome assessments, we have devised tele-outcomes to mitigate in-person contact. These outcome assessments would replace in-person assessments during COVID-19 precautions. We may resume in-person outcomes once COVID-19 recommendations are lifted.

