We would ask participants to send a picture or video confirmation that they are taking their blood pressure with their blood pressure cuff. Around these 6 and 12 month assessments, text messages and/or phone calls will be sent to participants to facilitated the tele-outcome assessment scheduling. Participants may be mailed a reminder, and instructions sheet of how to complete this assessment appropriately, with the least amount of PHI possible (Appendix M and N). These materials may be mailed out by a HIPAA compliant mail service. Participants may also be directed to a video through text message link or website which is demonstrating how to take a picture of cuff, and sending it in (<https://www.youtube.com/channel/UCup3LoqlxtMw9sYHQEX7AIA> available at reachouted.com). These resources may be visually modified, rearranged, or re-worded as resources or COVID-19 standards change, but the messaging, and content will remain consistent. These materials are included as appendices or links in the protocol, and will be submitted to the IRB as outlines of materials. However, time sensitive information, and content may change as needed to better communicate and stay up to date with participants. Given the topics and theme of the content will remain consistent, we will not submit changes to the IRB unless there are significant additions or deviations from topics.

In these tele-outcomes, participants may complete outcome assessments in the following ways. We may ask the participant to include a picture, or video of themselves taking their blood pressure when they text in their BP. This could be texted, emailed, postal mailed, or another means available to the participant, as we are attempting to be equitable between participants according to their availability for method. We will utilize all secure means to assist in these outcomes and promote equity in completion between participants (this may include phone, text, facetime, blue-jeans, text link to youtube tutorial, etc). Participants will also be instructed to text message in 3 consecutive measures and adhere to the American Heart Association best practices for measuring blood pressure. Reach Out will attempt to complete the outcome survey via phone, mail, or similar means. If participants are unable to send pictures based on their phone service, we may use methods such as mailing a disposable camera with returned mailing for their use, or having them ask a friend to text it to us.

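### The tele-outcome photo shows a cuff on a wrist, not a reading, so 12-month SBPs collected remotely are typed values that no required step verifies

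*Protocol*

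**What the plan says.** Protocol section 7.1.2 (Tele-Outcomes) covers the 6- and 12-month assessments: "These outcome assessments would replace in-person assessments during COVID-19 precautions". Return to in-person visits is left open: "We may resume in-person outcomes once COVID-19 recommendations are lifted". The image is meant to confirm the act of measuring ("We would ask participants to send a picture or video confirmation that they are taking their blood pressure with their blood pressure cuff"), and the values come separately: "Participants will also be instructed to text message in 3 consecutive measures". Video, live video contact and staff help are mentioned as possibilities, not requirements.

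Appendix N turns this into participant steps. Steps 1 and 2 are to photograph the cuffed wrist and send the photo: "We only need to see your wrist and that the cuff is on your wrist". Step 3 is to measure and text three blood pressures: "This is a text message and does not have to be a picture". The printed guide is the 6-month sheet ("It is time for your 6- month outcome"). Its use at 12 months follows from section 7.1.2 and from the 12-month letter in Appendix M ("It is time for your 12-Month Reach Out outcome measurement"), which refers to instructions on the next page.

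The primary endpoint (protocol 1.1, SAP 2.4) is the SBP reduction to 12 months from the median of three eligibility-phase readings. The SAP is dated September 2018, before tele-outcomes were added in March 2020, and has no analysis by mode of measurement.

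**The concern.** The photo is complete before any reading exists. It shows that a cuff was worn. It says nothing about the three numbers that follow. A participant can round, choose among several readings, or type a value without measuring, and still satisfy every required step. Appendix N asks for three different readings where section 7.1.2 asks for consecutive ones, and this leaves some room for choice.

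Neither document describes blinding, but participants necessarily know whether they receive healthy-behavior texts, daily or weekly prompts, and scheduling help. Some of the texts in Appendix D praise progress. If the tendency to report a favorable value differs between the two levels of a component, the difference is added to that component's effect. The stratification covariates do not remove it, and nor does a simple term for mode. Components that pass the 0.10 bar go forward to the next trial, so a false signal would carry over.

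**Working it through.** **1. Which values are affected.** Only 12-month SBPs collected by tele-outcome. No count is given. Section 3 dates the intervention period from March 2019, the February 2020 newsletter (Appendix L) says outcome visits were just beginning, and the tele-outcome amendment is dated 16 March 2020. A large tele share is therefore likely, but this is inference.

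**2. The plan's own figure.** Protocol 9.3 requires 196 participants for 80% power, alpha 0.10, on an effect of 1 mm Hg with SD 2.8. Taken two-sided, as the SAP reports p-values:
- Standardized effect 1/2.8 = 0.357, which the protocol writes as 0.35.
- Normal approximation: total N = 194.
- Noncentral t with 7 parameters (intercept, three main effects, three two-way interactions): power 0.801 at N = 196.

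The figure reproduces, so these inputs can be used to size the concern.

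**3. Size of a reporting bias.** For one component,

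bias = f × p × m,

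where f is the share of completers assessed by tele-outcome, p is the excess proportion shading their value at one level compared with the other, and m is the mm Hg shaded. The documents give none of the three. Assumed ranges: p = 5–15%, m = 5–10 mm Hg.

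| f (assumed) | Low: p = 0.05, m = 5 | High: p = 0.15, m = 10 |
|---|---|---|
| 0.25 | 0.06 | 0.38 |
| 0.50 | 0.13 | 0.75 |
| 1.00 | 0.25 | 1.50 |

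For f = 0.50: 0.50 × 0.05 × 5 = 0.125 and 0.50 × 0.15 × 10 = 0.75 mm Hg.

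**4. Effect on the test.** With 240 completers and SD 2.8, SE = 2 × 2.8/√240 = 0.361 mm Hg. The two-sided 0.10 threshold is 1.645 × 0.361 = 0.59 mm Hg. With no true effect, the chance of significance is 1 − Φ(1.645 − bias/SE) + Φ(−1.645 − bias/SE):
- bias 0.125: 0.097 + 0.023 = 12%
- bias 0.5: 40%
- bias 0.75: 67%

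The nominal rate is 10%. At larger assumed SDs of 10, 15 and 20 mm Hg, a bias of 0.5 gives 12.5%, 11.1% and 10.6%. The test then reacts less, but the estimate is shifted by the same number of mm Hg.

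**5. Equal shading.** If both levels shade equally, the main effects are not biased. The arm 1 change, which the plan examines if no component is significant, would still be biased unless the same shading was present at baseline.

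**The case against.** The strongest reply is that the baseline is of the same kind. The three eligibility-phase readings are self-measured and texted without a photo (section 5.3.4), so typed 12-month values match the baseline mode, and values read from a display would not. This is a fair reason to record mode. It does not answer the concern, because baseline readings precede randomization and their error cannot depend on assigned component, while 12-month reporting can.

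Second, differential reporting is plausible but not shown. There is no untreated arm; everyone has a cuff, training and prompts; and nothing tells participants which level is favored. This stands, and it is why the size can only be a range.

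Third, section 7.1.2 permits video and live contact, Appendix N offers a staff walk-through, and Appendix A says to send the first reading. These may verify or discipline some values, but none is a required check. The supplement for 15 and 18 months (Appendix Q) says the photo would ideally include the measurement but puts cuff placement first, which looks like a deliberate choice about burden. Retention was already below expectation, so burden matters.

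Three stronger readings are tempting:
- That the whole primary endpoint is unverified self-report. In-person 12-month values are not affected, and those visits may resume.
- That the photo already requested could have captured the readings. One photo taken beforehand cannot show three later values; the steps would have to be reordered.
- That the bias equals the 1 mm Hg minimal effect. This needs, for example, 10% × 10 mm Hg with every completer tele-assessed, and no document figure supports it.

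**Conclusion.** The point holds for 12-month SBPs collected by tele-outcome: no required step verifies the values, and reporting that differs by component level would bias that component's effect. With half of completers tele-assessed and the assumed shading, the bias is 0.13–0.75 mm Hg. This is below the 1 mm Hg that the protocol treats as the smallest relevant change, but at its upper end it exceeds the 0.59 mm Hg significance threshold implied by the protocol's SD. The direction and existence of such bias cannot be established from the documents. It is a cheap improvement to make, not a demonstrated flaw in the result.

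**What to change.** **Protocol.** Reorder Appendix N (6- and 12-month versions) and section 7.1.2 so that the photo or video is taken as a reading ends, with the cuff on and the display legible. Ask for this at least for the first reading and preferably for all three. Appendix A indicates that the device shows the value on its screen, and no face is needed. Keep the existing fallbacks, and keep accepting typed values when no photo can be sent, so that no outcome is lost.

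**Data.** Record each 12-month SBP as in-person, tele-verified or tele-typed.

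**SAP.** Keep all values in the primary model. Report mode by component level, and agreement between typed and displayed values. Add a sensitivity analysis by mode that lets the component effects differ between modes, since a mode term alone does not address differential reporting. Present any model restricted to verified values as supportive only: sending a legible photo is a post-randomization behavior that may itself differ by component.

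**Cost.** One reworded instruction sheet, one database field and one added analysis. Participants make slightly more effort, and some values stay unverified. If collection has closed, mode can still be classified where study records allow and the analysis run.

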Appendix Q- Supplement: Reach Out Cognition

[figure not shown]
Introduction and Background

We propose Reach Out Cognition which will extend Reach Out data collection past the current 12 months to 15 and 18 months. During Reach Out Cognition, we aim to assess novel approaches to mobile health (mHealth) self-administered cognition and blood pressure (BP) measurements. These approaches may include cognitive assessments via mobile applications (apps) and Web-based surveys, and wireless BP measurements via Bluetooth-enabled blood pressure cuffs and apps. The launch date is pending approval of a supplement and/or amendment and participant completion of the parent study 12-month outcome assessment (we anticipate July 2020).

Design

Recruitment:

The study population for Reach Out Cognition will be drawn from Reach Out participants who complete the Reach Out intervention and are defined as: participants who complete the 12-month outcome assessment. We anticipate about 240 participants will have completed Reach Out's 12-month outcome assessment and will be eligible for Reach Out Cognition. At the time of the final (12-month) outcome assessment, participants will be introduced to the opportunity of continuing for another ~6 months with the added mHealth measures.

Inclusion:

Participants of the Reach Out protocol that are no more than 6 months after completion of their 12-month outcomes are eligible. A subset of Reach Out participants will not have smartphones. However, our goal is inclusivity and generalizability and will allow for inclusion of all cell phones with the capability to send picture text-messages. Thus we designed Reach Out Cognition with the capability to include these participants, albeit outcome assessments procedures will differ.

Exclusion:

Participants who have withdrawn or not completed follow up visits.

Screening:

Prior to consent, participants may be screened for baseline cognition via the mini-Montreal Cognitive Assessment (MoCA) or similar. This would be preceded by verbal screening consent ([Appendix V](#)). Participants may either be given a feedback sheet in person, via postal mail, or text message to link regarding their MoCA score if fully completed ([Appendix S](#)). If score <11, or similar test specific cognitive threshold, we will state the MoCA suggested response to this range, and participant will not be consented for the study. It will be suggested that participant may wish to share the MOCA score with their doctor to discuss memory and thinking. Participant's doctor will be able to answer questions and decide whether more testing or treatments are right. These tests are not diagnostic.

Consent:

If 12-month outcome is in-person, and the participant agrees to continued participation, an informed consent will be signed (may be electronic and built into redcap as previous informed consent) by the participant before any study procedure is done.

However, in the time of COVID-19, the consent process and subsequent surveys may also be done virtually, if performing a 12-month outcome via tele-outcome per Reach Out protocol. In this circumstance, we would perform remote recruitment and consent. The research staff will follow a phone consent script ([Appendix R](#)), this may be done with whatever means best possible for participant (telephone, video, etc). The research staff will ask for the last name, and month and year of birth as confirmation that we are speaking to expected patient. Only once confirmed, will the research staff begin the process of consent. The consent process will be performed by the research staff in a private environment to provide the most privacy possible. The research staff will explain the study to participants during the consenting process. Interested participants will be enrolled in the study after providing verbal consent (for remote recruitment). The research staff will discuss questions with the participant, and research would only begin after informed consent is obtained.

For participants who are within 6 months of their 12 month visit but have completed their 12 month outcome visit prior to approval of this amendment, we may attempt to re-contact them to perform remote recruitment and consent.

For feasibility reasons, within our already approved waiver of hipaa authorization, we add waiver of documentation of informed consent to allow for the study enrollment consenting to be obtained in multiple ways (i.e., in-person when feasible, or verbal consent for those completing remotely).

We will give the participant a copy of the informed consent document. Given this is a study of no more than minimal risk of harm, and seeking in-person written consent may prove more harmful to participants, we will also seek a waiver of documentation of consent in the case tele-outcomes are being done. In this circumstance, we would read an informed consent script over the phone, discuss questions with the participant, and research would only begin after participant

verbally consents. All following enrollment training discussed would then be done over the phone or through video services, and materials would be either emailed, texted, or postal mailed to participant.

Enrollment:

After enrollment participants may complete a brief survey assessing their eHealth literacy via the eHealth Literacy Scale or similar and baseline cognition via the Self-Administered Gerocognitive Exam (SAGE). Participants will either be given a feedback sheet in person, via postal mail, or text message to link regarding score, which may only be sent out if the survey is fully complete, or it is determined than an appropriate score can be calculated based on missing values (Appendix S). If score <17, we will state the SAGE suggested response to this range. It will be suggested that participant may wish to share the SAGE score with their doctor to discuss memory and thinking. Participant's doctor will be able to answer questions and decide whether more testing or treatments are right. These tests are not diagnostic.

Participants will receive a BP arm cuff and incentives for completing the outcome assessments. They may also receive materials helpful in technology assistance and instructions. These may be mailed or emailed to participants if performing tele-outcomes.

At enrollment, participants will undergo about a 60-minute technology introduction tailored to if they have a smart phone or a feature phone. Reach Out Cognition assessments will differ based on whether the participant has a feature phone or smartphone (Table 1). If participant phone capabilities change throughout the duration of the study, we will work with them to re-train on their new phone.

- Feature phones include capabilities such as built-in cameras.
- Smartphones, in comparison, have touch-input and advanced computing software, in addition to built-in cameras, apps, and Web-browsers.

Participants will receive a Bluetooth-compatible BP monitor, the Omron Evolv Wireless Upper Arm Home BP Monitor or similar model which may depend on phone capability.

Table 1: Overview of Reach Out Cognition and BP Assessments		
Data	Smartphone	Feature Phone
SAGE	Texted survey for phone-use	Texted survey URL for browser-use
Neuro-QoL	Texted survey for phone-use	Texted survey URL for browser-use
BP	App and Bluetooth BP cuff	Texted BP with photograph

We will review procedures and trainings for all groups and phone capabilities. Those with smartphones may download the necessary app associated with the Bluetooth-compatible BP monitor. This will allow participants' blood pressures to directly sync the BP cuff to the app.

Participants with feature phones will be trained on how to photograph the process of obtaining BP measurements and how to submit the picture via text to the study team. While, ideally it would include the BP measurement, we are most interested in confirming the BP cuff is on the participant's arm as a measure of validity of the measurement. The picture does not have to include the persons face or any identifiers.

We will also review best practices for BP measurements. Participants will receive a text to an online survey link for survey questions. This link can be used directly, or typed into a web-browser. The participant and the study coordinator may complete a mock round of cognitive and BP measures in the practice environment to identify and solve any technological issues. If enrollment is not able to be done in-person, training would then be done over the phone or through video services, and materials would be either emailed, texted, or postal mailed to participants. We will have participants download the app (if able) while we are communicating with them, so we may train them in set-up and use of both app, text messages. We will postal mail the blood pressure monitor to participants, and then may also have another virtual training with participant in blood pressure monitor use.

We will also have resources and trainings available on the Reach Out website (reachouted.com) accessible to participants (for example, Appendix T and Appendix U).

Intervention

Participants who agree to continue in Reach Out Cognition will continue to receive the Reach Out intervention at a moderate intensity; this may include daily healthy behavior text messages and weekly prompted blood pressure self-monitoring. We elected to forego facilitating the primary care appointment scheduling and transportation as that was not automated and thus requires substantial study team resources and is not consistent with Reach Out Cognition's solely mHealth intervention.

Reach Out Cognition, will extend data collection to include 15 and 18 month assessments +/- 45 days for contact for outcomes. These assessments may include mHealth cognition and blood pressure assessments (Figure 1). Cognitive measures may be assessed using two different validated measures (or similar methods): 1) SAGE; and 2) Neuro-QoL-Cognition (Quality of Life in Neurological Disorders). Self-reported blood pressure outcomes will be based on either pictures or a Bluetooth-enabled BP cuff.

Outcomes (smartphone and feature phones)

At around 15 and 18 months, participants will receive reminder text message(s) and/or email(s) to complete a survey link and/or variations of computer adaptive assessment, or paper copies of survey, to either be mailed back or take a pictures and text/ email to return. In either scenario, the survey information does not contain sensitive information, and our attempt is to be flexible in receiving outcomes as is preferable and feasible from participants. The survey link may directly import data into RedCap or another equivalently secure database. Participants may also be

mailed and called as reminder(s) for these outcomes, and to assist with technology troubleshooting.

Participants with smartphones will be sent a reminder text message to complete a Bluetooth enabled BP measurement. In order to get the data, we will train participants on how to download their data via the Bluetooth app, and send the data to the study team either text or email to a secure study team email. If the sending of data method is unavailable, or is found to be too difficult for participants, the study team will conduct an in-person or virtual outcome visit to download final blood pressures from the Bluetooth app or collect BP measurements over the phone.

Participants with feature phones will be sent a reminder text message prompting the photograph blood pressure procedure. We will ask the participant to include a photograph of themselves taking their blood pressure when they text in their BP. We will instruct participants to send the picture, and text message 3 blood pressure measurements. Participants will be instructed to take 3 consecutive measures and adhere to the American Heart Association best practices for measuring blood pressure. This will be done via secure texting via Mosio. If the sending of data method is unavailable, or is found to be too difficult for participants, the study team will conduct an in-person or virtual outcome visit to for assistance or collect BP measurements over the phone.

Participants who do not respond to outcome requests or indicate technical difficulties, may be contacted by the study team via phone or text to troubleshoot.

Participants may be contacted to invite them to participate in other mHealth or stroke prevention trainings, if interested.

Throughout the duration of the intervention, the study team will attempt to support and connect with the participants as able. All resources, materials, and methods of contact are included as appendices or standards in the protocol, and will be submitted to the IRB as outlines. However, time sensitive information, and content may change as needed to better communicate and stay up to date with participants, especially given COVID-19, and the changing standards of interactions. Given the topics and theme of the content will remain consistent, we will not submit changes to the IRB unless there are significant additions or deviations from topics or methods.

Data Security

Reach Out will use a secure, password-protected web-based application, REDCap and/or qualtrics, for data collection and surveys. The text messages and picture messages are within a SSL encrypted web-based application with secure log-ins to access. The Bluetooth app is subject to the terms and conditions of the particular company, which will be presented to the participant. The data being utilized on these apps (blood pressures) will only be connected with personal information if the participant chooses to use their name and email in the profile description and sharing capability. Regardless, additional personal identifiable information will not be associated with the blood pressures or the app from Reach Out. Additionally, any data submitted by participants via direct download from BP app and sent to study team by email correspondence will be through a secure study team email. Only Reach Out study team members will have access to the study email account. All data submissions received on the study email account will

be transferred to the password-protected database. All Reach Out study team members will receive data security training.

Outcomes

We will measure acceptability, feasibility and satisfaction which are necessary for large scale use of mHealth BP and cognition measures. We will use these scales or similar validated measures of acceptability, feasibility and satisfaction.

Acceptability is the perception among participants that the mHealth assessments are achievable and agreeable. Acceptability will be assessed by the proportion of Reach Out 12-month outcome participants who continue into Reach Out Cognition.

Feasibility is the extent to which the mHealth assessments can be successfully carried out. Feasibility will be assessed by the proportion of participants who complete the mHealth cognitive assessment and the BP assessments separately. We will declare feasibility if greater than 50% of participants provide at least one cognitive measure.

Satisfaction is the perception that upon completion of the mHealth assessments participants found them agreeable. Satisfaction will be measured with a text survey to all participants. The satisfaction survey is 4-item, written at a 5th grade reading level and takes less than 5 minutes to complete. Responses are a 5 item likert scale. In addition, we may invite a subset of participants to participate in a focus group.

Focus Groups

To assess participant satisfaction with mHealth self-administered cognitive and blood pressure measures, we may conduct up to 4 focus groups of about 10 participants each of Reach Out Cognition. We anticipate the focus group to last about 60 minutes and will be conducted at a location convenient to the participants or virtually via secure means provided by the University of Michigan (<https://safecomputing.umich.edu/dataguide/?q=home>). Focus groups will be based on a semi-structured interview guide. Given this is minimal risk, and conversational, this will not be submitted to the IRB. During the focus group team members will assist in taking structured notes. Participants will be given \$25 in appreciation of their time.

Analysis

Descriptive statistics will be used to evaluate acceptability, feasibility and satisfaction. The denominator is the number of Reach Out participants who complete the 12 month assessments. Regarding feasibility, we will separately determine the feasibility by mHealth measure (i.e. cognition vs. BP), phone type (i.e. smartphone vs. feature phone) and operating system type (iOS vs. Android vs. Windows) as a continuous and dichotomous (>50% completion of each assessment type) measure. The satisfaction scale will be assessed for all participants. Given the difference in procedures by phone type, we will compare satisfaction between the smartphone and feature phone users using a Kruskal-Wallis test.

Minorities and women: Per NIH policy, the primary outcomes will be analyzed for evidence of differential treatment effects in subgroups determined by sex/gender, race, and ethnicity.

Upon recruitment during the parent study final outcome visit, we may collect a Montreal Cognitive Assessment (MoCA). We anticipate that approximately 10-20% of our participants will have previously undiagnosed mild cognitive impairment. In addition, using the Neuro-QOL cognition battery, we will determine how much the Reach-Out Cognitive cohort differs from the expected values for the patient reported outcomes. Using existing data on trajectory of change in MoCA based on age, we will develop estimates of the likely cognitive status of ED patients with hypertension 12 months prior to enrollment in Reach Out Cognitive (i.e. at the time initially seen in ED and enrolled in the parent Reach Out trial).

